4.1.3 Exclusion Criteria

Candidates will be excluded from study entry if any of the following exclusion criteria exist at the time of study entry:

- Severe weakness in bilateral upper limbs causing complete loss of function
- History of severe allergic or anaphylactic reactions or known drug hypersensitivity
- Female subjects considering becoming pregnant while in the study
- Female subjects who are currently pregnant or breast-feeding
- Unwillingness or inability to comply with the requirements of the protocol including the presence of any conditional (physical, mental or social) that is likely to affect the subject's ability to comply with the protocol.
- Active HBV infections
- Prior treatment with Ocrevus™
- Severe tremor/ataxia of the UE as defined by an EDSS with Cerebellar Functional System score of 3 or more due to upper extremity score (moderate tremor or clumsy movements interfere with function in all spheres)

- Severe spasticity of the UE as defined by EDSS, Pyramidal Functional System score- Upper Limb spasticity subscore of 3 or more (severely increased muscle tone that is extremely difficult to overcome and full range of motion is not possible)
- Cognitive impairment that may interfere with the conduct of the necessary testing (determined by the investigator)
- Any other reason that, in opinion of the Investigator and/or the Sponsor, the subject is determined to be unsuitable for enrollment in this study

4.2 METHOD OF TREATMENT ASSIGNMENT

There is no randomization in this study. Stratification of results by age and baseline UE strength may occur in the analysis.

4.3. STUDY TREATMENT

Ocrelizumab will be provided commercially to patients that participate in this study.

4.4 CONCOMITANT AND EXCLUDED THERAPY

Physical therapy will be documented and any other ongoing medications.

4.5 STUDY ASSESSMENTS

4.5.1 Overview of Study Visits

Screening/Baseline Visit (Day 0)

After the ICF is signed, the following information/assessments will be conducted:

- Review of medical history
- Review of inclusion/exclusion criteria
- Documentation on concomitant medications
- Demographic information
- Vital signs
- Measurement of UE function (TEMPA, 9HPT)
- Questionnaires (UEFI, FSS, SDMT, MUSIQOL)
- Physical examination/EDSS

Quarterly Visits* (Months 3, 9, 15, 21)

- Changes in concomitant medications and AE
- Questionnaires (UEFI, FSS, SDMT, MUSIQOL)
- Vital signs
- Interval history

*In the case of financial or physical limitations with the patient, the quarterly visits will be conducted via phone. In these instances, vital signs will not be obtained, as this will not affect the standard of care.

Semi-annual visits (before Ocrevus[™] infusion) (Months 6, 12, 18)

- Changes in concomitant medications and AEs
- Review of concomitant medication and AEs
- Questionnaires (UEFI, FSS, SDMT, MUSIQOL)
- Physical examination/EDSS
- Vital signs
- Interval history
- Measurement of UE function (TEMPA, 9HPT)

Month 24 End of study (EOS)/Early discontinuation visit

In the event Ocrevus[™] is discontinued prior to the end of the 24-month study, the patient will be asked to come in for EOS procedures. Any AEs attributed to Ocrevus[™] in the opinion of the investigator, will be followed until resolved, and documented in the patient study chart.

- Review of concomitant medication and AEs
- Patient questionnaires (UEFI, FSS, SDMT, MUSIQOL)
- Physical examination/EDSS
- Vital signs
- Interval history
- Measurement of UE function (TEMPA, 9HPT)

4.6 DISCONTINUATION OF COMMERCIAL THERAPY

In the event Ocrevus[™] is discontinued prior to the end of the 24-month study, the patient will be asked to come in for EOS procedures. Any AEs attributed to Ocrevus[™] in the opinion of the investigator, will be followed until resolved, and documented in the patient study chart.

4.7 SUBJECT DISCONTINUATION

If a patient discontinues use of Ocrevus, for any reason, they will be asked to attend an EOS visit to conduct final assessments (same format as month 24 visit).

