3.3.1 Primary Outcome Measure

No significant change in UE function over 24 months after initiation of Ocrevus™ measured objectively by measure of time to completion (seconds) and functional

scores on TEMPA (0 to -3). The hypothesis is that there is (stabilization) no significant change (within 20%) of TEMPA score from baseline to 24 months

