4.9.3 Efficacy Analysis

a. Primary Endpoint

1. TEMPA scores after 24 months of Ocrevus[™] treatment. Paired sample t-test to compare the 24 month measurements to the baseline measurements.

Mean within-patient changes from baseline through 24 months (TEMPA). Oneway repeated measures ANCOVA for TEMPA scores from baseline, 6 months, 12 months, 18 months, 24 months which will account for baseline characteristics (baseline disability level). A soft stratification will be applied so that recruitment will aim to include a spread of types of patients, those below overall EDSS of 6.0 and those above 6.0. If more than 2/3 of total enrollment is in one of the categories, the study team will reestablish efforts to recruit for the other cohort.

If data does not have normal distribution, then other non-parametric analysis will be employed (such as sign test for TEMPA functional score).

The threshold to determine a significant clinical change will be >20% from baseline value. This clinically significant difference is estimated based on data from the Oratorio trials that showed progression among both groups (placebo and OcrevusTM) but to a lesser extent in the OcrevusTM arm with an established clinically significant threshold of 20% (data will be requested from sponsor for use to review 9HPT results for the abnormal function at baseline group of patients). Measures will be collected and analyzed as units of time (seconds) and as functional scores on an ordinal scale that range from 0 to -3 (0 indicating

no signs of dysfunction).Ad hoc analysis may occur that includes evaluation of patients with significant clinical changes versus those that did not have significant clinical change based on any of the subscales within the TEMPA or physical exam. We will review >15%, >20% and >25% [in better hand and in worse hand] change from baseline with increases in time implying clinical progression and stability or decrease in time implying stability or improvement in function

b. Secondary Endpoints

Pearson correlation coefficients will be calculated to evaluate correlations between UE function (measured by TEMPA and 9HPT) primarily at baseline but also at each time point over the 24-month time period to compare patient responses on the UEFI, FSS, and MUSIQOL. Correlations with the primary endpoint scores and the SDMT will also be analyzed for any indication of new cognitive impairment that may interfere with the interpretation of the results.

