4.9.5 Missing Data

Study staff will work to ensure missing data is minimized. If there are less than two percent of time points missing, then during analysis, last value carry forward imputation will be used. If greater than two percent missing, multiple point imputation measures will be used.

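### Upper-extremity assessment ends when Ocrevus is stopped, so month-24 TEMPA and 9HPT are not collected for those patients and no rule says how they enter the analysis

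*Combined protocol and SAP*

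**What the plan says.** All references are to the combined protocol and SAP.

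- **Follow-up after stopping.** Section 4.7: "If a patient discontinues use of Ocrevus, for any reason, they will be asked to attend an EOS visit to conduct final assessments". The visit has the month-24 format. Section 4.6 repeats the arrangement. Section 4.5.1 puts both occasions under one title, "Month 24 End of study (EOS)/Early discontinuation visit", and lists TEMPA and 9HPT among the procedures. The only follow-up described beyond that visit is of adverse events that the investigator attributes to the drug. Appendix A has no column or footnote for patients off drug.
- **Primary outcome.** Section 3.3.1: "No significant change in UE function over 24 months after initiation of" Ocrevus, with the hypothesis of a change within 20% "of TEMPA score from baseline to 24 months".
- **Primary analysis.** Section 4.9.3: "Paired sample t-test to compare the 24 month measurements to the baseline measurements", plus a repeated-measures ANCOVA on "TEMPA scores from baseline, 6 months, 12 months, 18 months, 24 months". The cut-off is also there: "The threshold to determine a significant clinical change will be >20% from baseline value". The same section labels the endpoint as TEMPA following 24 months on the drug, which is not the same as 24 months from initiation.
- **Proportion stable.** Section 4.9.6 adds the percentage of patients who stay within 20% of baseline as a quantity of interest.
- **Missing data.** Section 4.9.5: with under 2% of time points missing, "last value carry forward imputation will be used"; above 2%, a multiple imputation is named without a model. Section 4.9.1 says only that imputation may be used if much is missing.

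**The concern.** The early visit takes the month-24 slot. A patient who stops at, say, month 8 therefore has a TEMPA at the stop and nothing after it, while the primary comparison needs a value at month 24. The gap is created by the design, not by patients declining to attend.

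Three things follow. Change between the stop and month 24 is unobserved. The plan does not say whether the TEMPA at the stop stands in for month 24, serves as an intermediate value, or is set aside. And the planned imputation must fill the gap either by assuming no further change (carry-forward) or by borrowing largely from patients still on drug (multiple imputation with no model stated).

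The study has one arm and its claim is stability. Section 3.2 expects disability progression to be visible within two years. If patients who stop do worse afterwards than those who continue, both routes push the result towards the study's own hypothesis, and there is no comparator in which the same bias would appear.

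**Working it through.** **Plan's own figures.** There is none to reproduce. Section 4.9.6 says the sample size is not calculated and gives no dropout rate. It plans data on 30 patients with up to 35 screened: 1 - 30/35 = 14.3%. That margin covers screen failures and withdrawals together, so it is not a stopping rate.

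**Step 1: which missing-data rule would apply.** TEMPA is scheduled at 5 time points (baseline and months 6, 12, 18, 24). For 30 patients that is 30 x 5 = 150 values, or 30 x 4 = 120 after baseline. The plan does not say which denominator counts.

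- One patient stopping after month 6 can miss months 12, 18 and 24: 3/150 = 2.0%, which neither rule covers, or 3/120 = 2.5%, which goes to multiple imputation.
- Two patients missing month 24 only: 2/120 = 1.7%, which goes to carry-forward.

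So carry-forward governs only when almost nobody stops. Otherwise the unspecified multiple imputation does.

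**Step 2: range with no assumption about how stoppers fare.** With k of 30 patients lacking month 24, the stable proportion over all 30 can lie anywhere in an interval of width k/30. The number of stoppers is assumed, as is a stable rate near 80% in completers.

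| Stoppers | Completers stable | Completers only | All 30, stoppers all not stable | All 30, stoppers all stable | Width |
|---|---|---|---|---|---|
| 3 | 22 of 27 | 81.5% | 22/30 = 73.3% | 25/30 = 83.3% | 10.0 points |
| 6 | 19 of 24 | 79.2% | 19/30 = 63.3% | 25/30 = 83.3% | 20.0 points |
| 9 | 17 of 21 | 81.0% | 17/30 = 56.7% | 26/30 = 86.7% | 30.0 points |

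**Step 3: illustrative bias of a completers-only proportion.** Let d be the fraction stopping, s the fraction of stoppers stable at month 24, and 0.80 the assumed rate in continuers. Then

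0.80 - [0.80(1 - d) + s x d] = d x (0.80 - s).

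| d | s = 40% | s = 60% | s = 80% |
|---|---|---|---|
| 10% | 4 points | 2 points | 0 |
| 20% | 8 points | 4 points | 0 |
| 30% | 12 points | 6 points | 0 |

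If s exceeds 80%, the sign reverses.

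**Step 4: the paired t-test.** The same logic applies to a mean: carrying the value at the stop forward misses d times the mean change after the stop. The plan gives no standard deviation or expected change, so this cannot be put in points.

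**The case against.** Several objections have force.

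- **Worsening before the stop is not lost.** A reader might infer that the worsening patients simply vanish. They do not: TEMPA and 9HPT are taken at the early visit. What is lost is change after the stop, and patients who do not attend. This stands and limits the concern.
- **Stopping need not mean worsening.** A reader might infer that those who stop are the ones most likely to have declined. The documents give neither a stopping rate nor reasons. Section 5.2 ties confirmed upper-extremity worsening to clinical evaluation, not to stopping. A link is plausible, but it is an inference.
- **The target is not settled.** Section 3.3.1 counts from initiation, but section 4.9.3 speaks of 24 months of treatment. Under the second reading, ending assessment at the stop is a coherent on-treatment choice. This stands: the documents do not establish that off-drug values belong in the primary analysis. But the on-treatment reading restricts the endpoint to patients who remained on drug, and the plan does not say that it intends this.
- **The plan does not specify a completers-only analysis.** Section 4.9.5 calls for imputation, so step 3 is an illustration and not a forecast. Imputation that uses the TEMPA at the stop could recover part of the loss under stated assumptions; the plan states none.
- **Extra visits are a burden.** Semiannual visits are timed before infusions. Off drug they become research-only visits, for patients with EDSS up to 8.0 and for a test that a rater must observe. This is a real cost.

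None of this supplies the month-24 value or a rule for the early one.

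**Conclusion.** The structural gap is certain: month-24 TEMPA and 9HPT are not collected from patients who stop Ocrevus early, and the handling of their last value is undefined. The direction of any bias is conditional: stability is overstated if stoppers fare worse after stopping.

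The size is unknown. The assumption-free statement is the k/30 range: 10 points for 3 stoppers, 20 for 6. The 0 to 12 points in step 3 rest on an assumed 80% stable among continuers, 10-30% stopping, 40-80% of stoppers stable, and a completers-only comparison. A reader might take a positive overstatement as established; the documents do not support that, because it disappears when stoppers do as well as continuers.

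Sampling error in a pilot of 30 is also large (22 of 27 has an exact 95% interval of 61.9% to 93.7%), but a selective gap would not average out with more patients. The change is worth making because values not collected cannot be recovered later.

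**What to change.** 1. Amend sections 4.5.1, 4.6 and 4.7 so that a patient who stops Ocrevus keeps the early visit and is also asked to attend the remaining scheduled semiannual upper-extremity assessments where feasible, at minimum TEMPA and 9HPT at month 24. Record the date of and reason for stopping. This concerns data collection only and changes no treatment decision.
2. Reconcile sections 3.3.1 and 4.9.3: state whether the target is the change at 24 months regardless of treatment or the change on treatment. Report both analyses, and name which is primary.
3. In section 4.9.5, state how the TEMPA from the early visit enters each analysis.
4. Add a sensitivity analysis that counts stoppers without month-24 data as not stable.

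**Cost.** The planned 30 patients do not change, and the assessments are already scheduled. The price is protocol wording, retention effort, and some visits not tied to an infusion for disabled patients. Values after the stop may reflect another therapy, which is why both analyses are needed, and the stable rate may come out less favourable.

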4.8 STUDY DISCONTINUATION

Genentech Study Center, and the Principal Investigator has the right to terminate this study at any time. Reasons for terminating the study may include the following:

- The incidence or severity of AEs in this or other studies indicates a potential health hazard to subjects
- Subject enrollment is unsatisfactory

- Data recording are inaccurate or incomplete
- Study protocol not followed

4.9 STATISTICAL METHODS

4.9.1 Analysis of the Conduct of the Study

All protocol violations will be accounted for and summarized in the results and discussion. If there are large amounts of missing data imputation measures may be used.

Demographic information will be collected on all patients in order to present descriptive statistics of the population.

4.9.2 Analysis of Treatment Group Comparability

There is only one designated treatment group. Descriptive statistics of the baseline characteristics of the enrolled population will be presented in the final report and manuscript.

4.9.3 Efficacy Analysis

a. Primary Endpoint

1. TEMPA scores after 24 months of Ocrevus[™] treatment. Paired sample t-test to compare the 24 month measurements to the baseline measurements.

Mean within-patient changes from baseline through 24 months (TEMPA). Oneway repeated measures ANCOVA for TEMPA scores from baseline, 6 months, 12 months, 18 months, 24 months which will account for baseline characteristics (baseline disability level). A soft stratification will be applied so that recruitment will aim to include a spread of types of patients, those below overall EDSS of 6.0 and those above 6.0. If more than 2/3 of total enrollment is in one of the categories, the study team will reestablish efforts to recruit for the other cohort.

If data does not have normal distribution, then other non-parametric analysis will be employed (such as sign test for TEMPA functional score).

The threshold to determine a significant clinical change will be >20% from baseline value. This clinically significant difference is estimated based on data from the Oratorio trials that showed progression among both groups (placebo and OcrevusTM) but to a lesser extent in the OcrevusTM arm with an established clinically significant threshold of 20% (data will be requested from sponsor for use to review 9HPT results for the abnormal function at baseline group of patients). Measures will be collected and analyzed as units of time (seconds) and as functional scores on an ordinal scale that range from 0 to -3 (0 indicating

no signs of dysfunction).Ad hoc analysis may occur that includes evaluation of patients with significant clinical changes versus those that did not have significant clinical change based on any of the subscales within the TEMPA or physical exam. We will review >15%, >20% and >25% [in better hand and in worse hand] change from baseline with increases in time implying clinical progression and stability or decrease in time implying stability or improvement in function

b. Secondary Endpoints

Pearson correlation coefficients will be calculated to evaluate correlations between UE function (measured by TEMPA and 9HPT) primarily at baseline but also at each time point over the 24-month time period to compare patient responses on the UEFI, FSS, and MUSIQOL. Correlations with the primary endpoint scores and the SDMT will also be analyzed for any indication of new cognitive impairment that may interfere with the interpretation of the results.

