2. OBJECTIVES

2.1 PRIMARY OBJECTIVES

To measure for clinical stabilization (defined as no significant change (≤20%) from baseline of UE function in multiple sclerosis patients with upper extremity impairment treated with Ocrevus[™].

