3.3 OUTCOME MEASURES

- The UE function will be assessed every 6 months over 24 months to gauge for any small changes at certain intervals but to also have a sufficient length of time that can be compared in order to assess for any type of change over time. *
- Incidence of UE functional changes (improved, worsening or stable) with scores of time and performance on the TEMPA.
- In this group of patients (advanced disability) there is less concern with relapse rate reduction; relapses happen at a low rate. There is more concern regarding any loss of function, and we will focus on UE function. Studies like this would provide better data for this type of patient aiding in the process of selecting appropriate disease modifying therapy.

*UE function includes measures on the TEMPA, UEFI and 9HPT.

UEFI is subjective and answered by the patient. The Upper Extremity Functional Index (UEFI) is a self-administered questionnaire which measures disability in patients with upper extremity conditions. The questionnaire lists 20 activities and the patient gives a score to each based on the difficulty they have completing that activity. The scores given to the 20 questions are added to give a highest possible score of 80. The lowest possible score is 0. A lower score indicates that the person is reporting increased difficulty with the activities as a result of their upper limb condition. The change from baseline per patient and for group means will be analyzed. A clinically significant change is determined as a 12% change. [20]

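### The primary hypothesis is TEMPA change within 20% of baseline, but the tests named for it test zero change; the percentage stable has no interval and is not named as the deciding result

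*Combined protocol and SAP*

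**What the plan says.** Section 2.1 gives the objective: "To measure for clinical stabilization (defined as no significant change (≤20%) from baseline of UE function". Section 3.3.1 repeats the limit for the primary outcome: "The hypothesis is that there is (stabilization) no significant change (within 20%) of TEMPA score from baseline to 24 months". It covers both completion time and the functional score.

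Section 4.9.3 names three methods for the primary endpoint:
- "Paired sample t-test to compare the 24 month measurements to the baseline measurements";
- a one-way repeated-measures ANCOVA over baseline and months 6, 12, 18 and 24;
- if the data are not normal, "then other non-parametric analysis will be employed (such as sign test for TEMPA functional score".

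The same section uses the 20% limit to classify change: "The threshold to determine a significant clinical change will be >20% from baseline value". It also says "Measures will be collected and analyzed as units of time (seconds) and as functional scores on an ordinal scale", and plans a review of changes above 15%, 20% and 25% by hand.

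At patient level, section 3.3 lists "Incidence of UE functional changes (improved, worsening or stable) with scores of time and performance on the TEMPA". Section 4.9.6 plans to find the percentage of patients who stay within 20% of baseline. It states that the 30 patients are a pilot sample with no calculated size, and expresses the belief that stabilization can be analysed.

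**The concern.** The hypothesis is a statement of sameness within a margin, while the named tests look for a difference from zero. A non-significant result may mean little change or merely a noisy sample of 30. A significant result may be a small, consistent change well inside the margin. Agreement between the tests and the 20% limit depends on the SD and the number of patients, not on the limit.

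The output that does match the hypothesis, the percentage stable, has no confidence interval, and the plan does not say that it is the deciding result. No mean-level result is compared with 20%. A report could therefore hold a p-value and a percentage that point in different directions, with no rule for which one answers the primary question.

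Two details add to this. The limit is relative but time is analysed in seconds: over the 100 to 400 seconds that section 3.2 cites for MS patients, 20% is 20 seconds for one patient and 80 for another. The functional score has 0 as its best value, and percent change from a baseline of 0 is undefined.

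**Working it through.** **Inputs.** From the documents: n = 30 (section 4.9.6) and a limit of 20% (sections 2.1, 3.3.1 and 4.9.3). Assumed, because the documents give neither: two-sided 0.05, and the SD of change, shown over a range. There is no sample-size calculation to reproduce. The t-test is placed on the percent-change scale so that it can be compared with the limit.

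**1. Where the t-test turns significant (no SD assumed).** The boundary is |mean| = t(0.975, 29) × SD / √30 = 2.045 × SD / 5.477 = 0.373 SD. Setting this to 20% gives SD = 20 / 0.3734 = 53.6%. At any smaller SD, some mean changes below 20% are significant. At any larger SD, some above 20% are not.

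**2. Sign test.** With no ties, exact binomial: 20 of 30 patients in one direction gives p = 0.099, and 21 of 30 gives p = 0.043. The size of the changes plays no part.

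**3. How often the t-test and the limit disagree.** Non-central t, 29 df, non-centrality = true mean × √30 / SD.

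| Assumed SD | True worsening 20%: P(non-significant) | True worsening 10%: P(significant) |
|---|---|---|
| 20% | 0.04% | 75% |
| 30% | 6% | 42% |
| 40% | 25% | 26% |
| 60% | 58% | 14% |

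**4. A mean does not stand in for the percentage stable.** If changes are normal with mean 0, the share within 20% either way is 2Φ(20/SD) − 1: 68% at SD 20%, 50% at SD 30% and 38% at SD 40%. A mean change of zero is compatible with most patients lying outside the limit.

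**5. Precision of the percentage stable at n = 30 (Clopper-Pearson 95% CI).** 15/30 = 50% (31% to 69%); 21/30 = 70% (51% to 85%); 24/30 = 80% (61% to 92%); 27/30 = 90% (73% to 98%).

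**6. What a ratio with a 95% CI could show.** Let the true month-24/baseline ratio of TEMPA time be 1.0 and s the SD of the log ratio. The upper limit falls below 1.20 when the log mean plus 2.045 × (sample SD)/√30 is below ln 1.20 = 0.182. By non-central t with non-centrality 0.182 × √30 / s, the probability is 99.8%, 89.6% and 67.5% at s = 0.2, 0.3 and 0.4. If the whole interval must lie between 0.80 and 1.20, simulation with 400,000 draws gives 99.8%, 87% and 51%.

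**The case against.** The strongest reply is that the plan already answers its own question. Sections 2.1 and 3.3.1 tie the word significant to the 20% limit, section 4.9.3 does the same for clinical change, and section 4.9.6 names the percentage stable as an output. A reader might infer that the investigators will take a non-significant t-test as proof of stability. The documents do not say so, and the point does not rest on it. What remains is that the tests listed under the primary endpoint cannot address the hypothesis, and that the output which can has no interval and no stated priority.

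A reader might also infer that the definition of stable is in open conflict. It is not. Sections 3.3, 3.3.1 and 4.9.6 fit together as within 20% in either direction, with improvement separate. The loose wording is in the last sentence of the primary-endpoint text in 4.9.3, "change from baseline with increases in time implying clinical progression and stability or decrease in time implying stability or improvement in function", which can be read as counting a large improvement as stable. Section 3.2, which contrasts stability only with progression, leaves the same room.

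Nor do the documents support an inference that patients who can no longer complete a task vanish from the analysis. Section 3.3 scores such a task −3, the functional score is part of the primary outcome, and section 4.9.5 provides imputation for missing time points. Only the handling of the time measure is left open.

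It is also fair that this is an uncontrolled pilot of 30 patients, and that the disagreement rates depend on assumed SDs and run from negligible to large. That limits the consequence. It does not make a zero-change test suit a within-20% hypothesis, and an estimate with an interval is the natural result of a pilot.

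**Conclusion.** The point holds: the inferential methods named for the primary endpoint do not test the primary hypothesis. This follows from the text and from the 0.373 SD boundary, which needs only n = 30, the assumed two-sided 0.05 and complete data. How often the tests would mislead cannot be fixed from the documents. At a true mean worsening of 20%, the chance of a non-significant t-test runs from 0.04% to 58% over assumed SDs of 20% to 60%. The plan deserves credit for intending to report the percentage stable. Its shortfall there is the missing interval, the missing statement that this result decides, and one loosely worded sentence. This should be fixed before analysis; it is no reason to doubt the data collection.

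**What to change.** In section 4.9.3:

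1. Make the percentage of patients stable at month 24, on one named TEMPA time measure, the primary estimate, with an exact 95% CI. Set no pass mark, because the documents give no benchmark rate. Define stable once, and align the last primary-endpoint sentence with sections 3.3, 3.3.1 and 4.9.6. Count a patient who completed the measure at baseline but cannot complete it at month 24 as not stable.
2. For any mean-level statement, replace the zero-change t-test with the month-24/baseline geometric mean ratio of TEMPA time and its 95% CI, read against 1.20 (and against 0.80 if the limit is two-sided). State that p > 0.05 is not evidence of stability.
3. Analyse the functional score in points rather than percent.

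In section 4.9.6, replace the statement of belief with the precision that 30 patients give, for example 24/30 = 80% (95% CI 61% to 92%).

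The cost is wording in two sections, with no new visits, data or patients. The downside is that mean stability may not be shown if variability is high. Even with no true change, the upper 95% limit falls below 1.20 with probability over 99%, 90% and 67% at assumed log-SDs of 0.2, 0.3 and 0.4.

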4.9.6 Determination of Sample Size

It is expected that 30 patients will be eligible to enter this study during the proposed timeframe. This is a pilot study; the TEMPA is a more comprehensive assessment of upper extremity function which we will use in the analysis of this group of patients to evaluate what percentage remain stable (within 20% variation from baseline) and analyze correlations with other measures of upper extremity function (9HPT and patient perception using the UEFI). Therefore, this is not a calculated sample size as there is a lack of historical data available for this population and the modalities of testing we plan to utilize. We do not have historical data to gather estimates for an accurate power calculation. We plan to gather data on 30 patients but will screen up to 35 in case of screen failures or early withdrawals. Even with the limited calculations we believe that we will be able to analyze for a clinically meaningful lack of change (stabilization).

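### Section 4.9.3 names no lead between the paired t-test and the repeated-measures ANCOVA, and leaves the ANCOVA's covariate so open that its time test could refer to EDSS 0

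*Combined protocol and SAP*

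**What the plan says.** Section 3.3.1 sets the hypothesis: "The hypothesis is that there is (stabilization) no significant change (within 20%) of TEMPA score from baseline to 24 months".

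Under the primary endpoint, section 4.9.3 lists two analyses of mean change. One is a "Paired sample t-test to compare the 24 month measurements to the baseline measurements". The other is a "Oneway repeated measures ANCOVA for TEMPA scores from baseline, 6 months, 12 months, 18 months, 24 months which will account for baseline characteristics"; the one characteristic it names, in brackets, is the baseline level of disability. Neither is called the lead, and there is no rule for the case where they disagree.

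The section does not say whether disability level means EDSS, whether it is continuous or grouped, whether it is centred, or whether a time-by-covariate term is fitted. The only nearby clue is a recruitment target that splits patients into "those below overall EDSS of 6.0 and those above 6.0". Section 4.1.2 admits EDSS 4.0 to 8.0.

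Both TEMPA scales are in play: "Measures will be collected and analyzed as units of time (seconds) and as functional scores on an ordinal scale". There is also a fallback: "If data does not have normal distribution, then other non-parametric analysis will be employed (such as sign test for TEMPA functional score").

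On size, section 4.9.6 says: "We plan to gather data on 30 patients but will screen up to 35 in case of screen failures or early withdrawals". It states that the number was not calculated. No significance level is given.

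**The concern.** Two things are left open.

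First, the two analyses answer different questions. The t-test addresses the 24-month contrast in the hypothesis. The ANCOVA's time test has four degrees of freedom and asks whether any of the five visit means differ. With no lead named, a split result leaves the reader to choose.

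Second, the ANCOVA's time effect depends on choices the plan does not make. A classical one-group repeated-measures ANCOVA fits covariate-by-time as part of the model, and its time effect is then the change at covariate value zero. With raw EDSS, that is a value no enrolled patient can have.

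The direction of the hypothesis raises the stakes. In most trials a weak test hurts the claim being made. Here the hoped-for result is no significant change, so a test with little power can be read as support for it.

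**Working it through.** The plan gives no power, SD, effect size or significance level, so there is no figure to reproduce. From the documents: n = 30 (4.9.6), five visits (4.9.3), EDSS 4.0 to 8.0 (4.1.2). Assumed: EDSS mean and SD, two-sided 5% level, change in units of its own SD.

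**1. What the time test refers to.** For any within-patient contrast Z (for example month 24 minus baseline), the model with interaction is Z = a + b·x + error, with x the covariate. The time test is of a = 0. With raw EDSS, a is the mean change at EDSS 0. With EDSS minus its mean, a is the mean change at the average EDSS enrolled.

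**2. Standard error.** Var(a) is σ²[1/n + m²/((n−1)s²)] uncentred and σ²/n centred, where m and s are the EDSS mean and SD. The ratio of standard errors is √(1 + n·m²/((n−1)·s²)).

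- m = 6, s = 1.0: √(1 + 36 × 30/29) = √38.24 = 6.2.
- m = 6, s = 1.3: √(1 + 36/1.69 × 30/29) = √23.04 = 4.8.
- For scale, EDSS uniform on 4 to 8 in half-points has SD 0.5 × √((81−1)/12) = 1.29.
- Over m = 5.5 to 6.5 and s = 0.8 to 1.5, the ratio runs from 3.9 to 8.3.

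**3. Rejection rates.** Simulation of 30 complete patients, five visits, EDSS uniform on 4 to 8 in half-points, linear change, compound symmetry, 3,000 runs per row. Mean change is at EDSS 6, and slope is in SD of change per EDSS point. Both ANCOVA columns include time-by-EDSS.

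| Mean 24-month change (SD) | EDSS slope | Paired t-test | ANCOVA, centred | ANCOVA, uncentred |
|---|---|---|---|---|
| 0.53 | 0 | 78.5% | 71.7% | 7.2% |
| 0.8 | 0 | 98.9% | 98.1% | 10.7% |
| 1.0 | 0 | 99.9% | 99.9% | 15.1% |
| 0.8 | 0.133 (change proportional to EDSS) | 98.6% | 98.0% | 5.4% |
| 0 | 0.1 | 5.5% | 5.5% | 8.3% |
| 0 | 0.2 | 5.6% | 6.1% | 18.5% |
| 0 | 0.3 | 4.3% | 5.2% | 38.8% |

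The first four rows show lost power. In the proportional case the change at EDSS 0 is exactly zero, so the uncentred test stays near 5% however much patients worsen. The last three rows show the opposite error: no average change, yet rejection in up to 39% of runs.

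**4. Is the interaction essential?** In one simulated data set, a mixed model without visit-by-EDSS gave a month-24 effect of 0.881 (SE 0.189) both centred and uncentred. With the interaction it gave 0.881 (SE 0.187, p < 0.001) centred and 0.725 (SE 0.925, p = 0.43) uncentred. The problem arises only with the interaction.

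**The case against.** The strongest reply is that the harm needs three conditions the plan never states: EDSS as a continuous covariate, left uncentred, with a time-by-EDSS term. This stands. A reader might infer that the plan enters EDSS without centring, but the documents are silent on it, and many plans leave such detail to the analyst. If disability is a two-level factor, as the recruitment split could suggest, the time effect depends on the coding and EDSS 0 does not arise.

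The first-listed paired t-test is exactly the contrast of section 3.3.1 and is untouched by any of this. So it would be wrong to infer that the plan would hide a worsening; the t-test would still be reported. Nor do the documents say that the ANCOVA p-value decides stability. Stability is tied to a 20% threshold, and section 4.9.6 describes a pilot that looks at the percentage of patients who remain stable.

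Two other stronger readings also fail. One is that the ANCOVA would discard every patient missing a visit; section 4.9.5 plans imputation, so this does not follow. The other is that the error always favours stability; the last three rows of the table show that it can go the other way.

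What remains is that no lead is named, the omnibus test does not match the hypothesis, and the covariate is undefined. A mixed model is one acceptable choice among several, and naming the t-test as lead would also settle the ambiguity.

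**Conclusion.** The point holds as under-specification with a conditional hazard. That no lead analysis is named, and that the five-visit time test is not the 24-month contrast, follow directly from sections 3.3.1 and 4.9.3.

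The EDSS-0 problem is conditional on the three unstated choices. If they coincide, the time test's standard error is about 4.8 to 6.2 times larger (assumed EDSS mean 6, SD 1.0 to 1.3, n = 30). Power for a 0.8 SD mean change then falls from 98% to 11% in the simulation. The direction is robust, but the exact values rest on assumed inputs.

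Centring, or a better model, does not turn a non-significant test into evidence of stability within 20%. That has to come from the confidence interval set against the margin.

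**What to change.** In section 4.9.3:

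- Name the baseline-to-month-24 mean change with its confidence interval as the single lead mean-change estimate, separately for TEMPA seconds and for the functional score.
- Estimate it from a mixed model for repeated measures in place of the ANCOVA, with visit as a factor and all available visits used. Say how the imputation rule in section 4.9.5 then applies.
- Define baseline disability as baseline EDSS, centred at the sample mean, and state whether visit-by-EDSS is fitted. If it is, the lead contrast is the change at mean EDSS.
- Use a small-sample degrees-of-freedom correction. An unstructured covariance for five visits has 5 × 6/2 = 15 parameters for 30 patients, so name in advance a simpler structure to use if it does not converge.
- Keep the paired t-test as supportive.
- State how the 20% margin is expressed on the scale of each estimate, and read the confidence interval against it.

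The cost is a few sentences in the plan. No extra patients, visits or measurements are needed, and standard software fits the model.
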